3.2 Study Rationale

Systematic invasive pressure measurement in the thyroid compartment after surgery might detect a continuous increase in pressure which is often caused by a growing haematoma, indicating serious post-surgery bleeding at a much earlier time compared to state of the art diagnostic workflow. In routine clinical care, detection of serious hemorrhage depends on the patients alerting symptoms even if post-operative intermittent monitoring of vital parameters and wound conditions is performed according to current medical guidelines and local instructions. Device-based, continuous hemorrhage detection within 36 to 48 hours after surgery would allow to objectively measure an increase in cervical pressure before symptoms occur. The IP cannot prevent bleeding complications, but early detection of post-operative hemorrhage is important to avoid additional morbidity and potential mortality. Thus, the risk of serious complications like hypoxic brain damage and death caused by post-operative hemorrhage is minimized. In addition, the intervention team would be able to fine-tune necessary actions during the rescue procedure based on objective pressure values, e.g. the decision to open cutaneous sutures immediately or later in the operation theatre, and therefore reduce additional perioperative morbidity and increase patients' safety.

The IP claims to measure pressure in the cervical compartment following thyroid surgery reliably, accurately, and safely, and can monitor pressure continuously. Therefore, the device might be able to detect clinically relevant hemorrhage within 48 hours following thyroid surgery earlier and with better predictive values compared to detection in current routine clinical care. Within this study, the diagnostic accuracy of the IP will be assessed.

3.3 Benefit-risk Assessment

3.3.1 General risk assessment of the HEDOS trial

- The study is purely diagnostic without any pre-defined therapeutic intervention in the study protocol. No random assignment to therapies is performed in this one-arm diagnostic accuracy trial.
- The indication for thyroid surgery and the consent of the patient to this therapeutic approach are decided in routine clinical care prior to any HEDOS trial activities in the corresponding patient.
- All medical therapies are at the discretion of the treating physician according to applicable medical guidelines and local treatment policies. Treatments and procedures will be decided by the treating physician based on the individual medical status of each study patient without guidance by the study protocol.
- All medical devices with the exception of the IP diagnostic device and drugs which may be used within
 the study will be marketed products to be used in line with market authorisation as given in their Instruction For Use (IFU) or Summary of Product Characteristics (SmPC) and represent standard of care
 (SOC). This also applies to the medical procedures within the trial. Thus, adverse events resulting from
 therapies within the study are expected to occur in similar clinical manifestations and at comparable
 rates as the known adverse events of the approved therapies in routine clinical care.
- The IP is only used as an external small box fixed at the upper arm of the patient by a soft silicone bracelet. A sterile disposable compartment pressure probe is placed in the surgical area at the end of the routine thyroid surgical procedure just before wound closure and subsequently connected to the device (in case of surgery on both sides two pressure sensors have to be used but both connected to just one external device box). Potential risks of this equipment are local infections at the suture or in the surgical area comparable to the risks of wound drainage often used after thyroid surgical procedures in routine

clinical care. However, pressure sensor catheter and the suture are protected by adequate dressing and the sensor will be removed completely within 48 hours after wound closure without reopening the suture.

- The measurements of the IP are kept secret until the end of the trial and, therefore, do not affect treatment decisions.
- The HEDOS trial is therefore considered to generally represent a low structural risk profile by design with respect to additional adverse events compared to routine clinical care.

3.3.2 Assessment of the individual risk of study patients

- The individual risk of study patients by applied therapies within the trial is equal to the risk in routine clinical care since all therapies and treatment decisions will be in line with applicable medical guidelines and routine clinical care policies. Medical devices and drugs used within HEDOS except for the diagnostic IP are marketed products used in line with market authorisation, based on individual therapy decisions of the treating physician, and represent SOC. This also applies to all medical procedures performed within the trial.
- Additional individual risk may be added by the disposable compartment pressure probe(s) placed in the surgical area before wound closure. However, previous use of this equipment together with adequate dressing and complete removal within 48 hours after wound closure [19] did not lead to any local infection. The catheter is comparable to drains placed in routine clinical care in some hospitals in the surgical area.
- Thus, the additional individual risk for patients participating in this diagnostic study is deemed negligible.

3.3.3 General benefit of study patients

All patients participating in the HEDOS trial will have the benefit of careful standardised monitoring of their treatment and follow-up procedures by their study physicians as in routine clinical care but in addition undergo quality management by the CRO, the sponsor and the Steering Committee (SC) of the trial.

3.3.4 Individual benefit of study patients

Individual benefit of study patients compared to routine clinical care is not expected.

4. Study Objectives

The primary study objective of the trial is to evaluate the diagnostic accuracy, i.e. sensitivity and specificity, of the diagnostic IP in detecting clinically relevant hemorrhage within 48 hours following thyroid surgery using 12mmHg of pressure as binary cut-off. In addition, a three-level decision system based on two different pressure cut-offs (10 and 20 mmHg) will be established and validated assessing sensitivity and specificity.

A surgical intervention triggered by suspicion of a post-operative hemorrhage detected in routine clinical care which is intraoperatively confirmed as needed is considered as gold standard.

Secondarily, the safety of the use of the diagnostic IP is assessed.

Primary and secondary objectives are validated in a patient cohort most widely representing the routine clinical care population.

4.1 Primary Endpoint Parameters

There is a first co-primary endpoint pair and a hierarchically subordinated third endpoint. The third endpoint is only evaluated in a confirmative way if the first pair of endpoints leads to a significant result. The primary endpoints are defined as follows:

- EP1. Sensitivity and specificity (co-primary) of the IP for detection of clinically relevant hemorrhage within 48 hours following thyroid surgery using 12 mmHg of pressure as cut-off compared to detection in routine clinical care.
- EP2. Area under the Receiver Operating Characteristic (ROC) curve for detection of clinically relevant hemorrhage within 48 hours following thyroid surgery by the IP in a three-level decision system using 10 and 20 mmHg of pressure as cut-offs compared to detection in routine clinical care.

Clinically relevant hemorrhage following thyroid surgery" (=true disease) is defined as surgical intervention triggered by suspicion of a post-operative hemorrhage detected in routine clinical care which is intraoperatively confirmed as needed (gold standard of routine clinical care detection).

The three-level decision system referred to in EP2, EP4 and EP5 is detailed in section 5.

If sensor measurement in some study patients is stopped earlier than 48h after thyroid surgery, e.g. because of device problems or sensor removal, data will be censored at the time of last measurements available.

If sensor measurement in some study patients continues more than 48 hours after thyroid surgery data will be analysed until last data available.

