The IP will be used within the study for continuous measurement of pressure values and their digital documentation with alerts and pressure display off. Potential risks of this equipment are local infections at the suture or in the surgical area. However, pressure sensor catheter and suture are protected by adequate dressing and the sensor will be removed completely about 48 hours after wound closure without reopening the suture.

The IP (without market approval) shall be kept in a locked location with limited and controlled access only for authorized persons at the study site. It will only be used for patients enrolled into the study.

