12.1.2 Analysis of the primary endpoint

Analyses of the co-primary endpoints in the stage 1 diagnostic study are based on the population of all enrolled patients with subsequent index thyroid surgery. This corresponds to the intention to diagnose (ITD) principle, whereas missing or inconclusive values are imputed by false positive or false negative results, respectively [25]. In accordance with the ICH E9 guidelines, the analysis population of all these patients is defined as the "Full Analysis Set" (FAS).

In the first pair of primary hypotheses, sensitivity and specificity are considered as co-primary endpoints. They are combined via the Intersection-Union Test. The global null hypothesis can only be rejected if both individual null hypotheses of sensitivity and specificity are rejected. The corresponding first global alternative hypothesis states that the IP exceeds a pre-defined minimum sensitivity of 80% and specificity of 65%. The second primary global hypotheses, the second primary global hypothesis can only be evaluated in a confirmative way if the first global primary hypothesis leads to a significant result. The hierarchical order of hypotheses requires no adjustment of the type I error rate.

The analysis of the first global primary hypothesis contains the estimation of the resulting sensitivity and specificity of the IP according to the defined cut-off value of 12 mmHg. For the estimation, a mixed binary logistic regression model is used [26]: The binary test result represents the dependent variable, the true disease status is included as fixed effect. Additionally, a random-intercept is estimated for each centre. Sensitivity is estimated via the calculation of the marginal mean for a diseased individual (=surgical intervention performed which confirmed post-operative hemorrhage needing intervention). False-positive rate, which is the counter probability of the specificity, is estimated via the calculation of the marginal mean for a non-diseased individual. Twosided 95%-logit confidence intervals with p-values are reported.

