12.4 Patient Selection for Analyses

A patient is considered as enrolled into the current trial according to regulatory requirements as soon as the signed the informed consent form. All enrolled patients will be part of the safety population.

A patient is considered as measured as soon as he is enrolled, screened, index thyroid surgery as defined in the study protocol was performed, and pressure monitoring by the IP was started. All measured patients will be part of FAS and will be followed according to study protocol.

Refer to section 6.2.1 for additional details.

13. Access to Source Data / Documents

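### The protocol has two unreconciled rules for a recording that stops before 48 h without reaching 12 mmHg, and the choice between them can change the primary result

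*Protocol*

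**What the plan says.** Section 4.1 covers short recordings in the definition of the primary endpoints. "If sensor measurement in some study patients is stopped earlier than 48h after thyroid surgery", for instance through device problems or sensor removal, "data will be censored at the time of last measurements available". Recordings longer than 48 h are to be analysed to their end.

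Section 12.1.2 sets the primary analysis on the intention-to-diagnose (ITD) principle, under which "missing or inconclusive values are imputed by false positive or false negative results, respectively". The summary repeats this. The model is a mixed logistic regression: "The binary test result represents the dependent variable, the true disease status is included as fixed effect". It has no time axis.

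Section 12.4 puts in the full analysis set every patient in whom "index thyroid surgery as defined in the study protocol was performed, and pressure monitoring by the IP was started". A patient whose recording started and then stopped early is therefore in the primary analysis.

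Sensor removal time is described in different ways. Section 3.3.1 says "the sensor will be removed completely within 48 hours after wound closure"; section 7.1 says "the sensor will be removed completely about 48 hours after wound closure"; section 7.1.1 and Appendix VI give a run time of at most 48 h. Section 4.1 counts its 48 h from thyroid surgery, while 3.3.1 and 7.1 count from wound closure.

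**The concern.** Censoring belongs to time-to-event data. In a model of a positive or negative result it has to be turned into something else, and the protocol does not say what. It could mean that the patient counts as negative so far, that the patient is left out, or that whatever happens after the last measurement is disregarded. Section 12.1.2 points elsewhere: if a short recording without a crossing is missing or inconclusive, it is scored against the device.

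For a non-bleeder whose sensor fails after little observation, one rule yields a true negative and the other a false positive. For a patient who bleeds after the sensor has stopped, one rule yields a false negative, and the other may yield no event at all.

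The confirmatory decision on sensitivity and specificity, and with it the confirmatory test of the AUC that follows in the hierarchy, could then depend on which sentence the analyst applies. The pressure data stay hidden until the end of the trial, so the rule can still be fixed without knowledge of its effect. That is no longer possible once the data are open.

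**Working it through.** **Inputs (sections 12.1.2 and 12.2).** N = 1,470; prevalence 1.5%; 22 events; assumed sensitivity 99% and specificity 95%; success if the lower two-sided 95% limits exceed 0.80 and 0.65. Non-bleeders: 1,470 − 22 = 1,448. The share of short recordings is not given, so a range is shown.

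**The plan's own figure.** One-sample normal approximation with null variance, n = 22:

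power = Φ{[(0.99 − 0.80)√22 − 1.96√(0.80 × 0.20)] / √(0.99 × 0.01)} = Φ(1.08) = 0.859.

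The protocol states 86%. Also 22 / 0.015 = 1,467, against 1,470 stated. Both reproduce.

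**Sensitivity.** Suppose 22 bleeders, of whom 21 are detected. The other one bleeds within 48 h, but after the sensor stopped without a crossing.

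| Rule for that patient | Result | Lower 95% limit | Decision |
|---|---|---|---|
| 12.1.2: imputed false negative | 21/22 = 95.5% | 0.739 logit; 0.772 Clopper-Pearson; 0.782 Wilson | fails |
| 4.1 as negative so far | 21/22 = 95.5% | the same | fails |
| 4.1 as ignoring the later bleed (patient kept as a non-event) | 21/21 | 0.839 Clopper-Pearson | passes |

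- Logit limit for 21/22: ln(21/1) = 3.045; standard error √(1/21 + 1/1) = 1.024; 3.045 − 1.96 × 1.024 = 1.038, which back-transforms to 0.739.
- Clopper-Pearson limit for 21/21: 0.025^(1/21) = 0.839.
- For comparison, 22/22 gives 0.025^(1/22) = 0.846, a pass.

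At 21/21 and 22/22 the plain logit interval is undefined, so the exact interval is used there.

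As an assumption, let a share s of bleeders have an early stop without a crossing. The chance of at least one among 22 is 1 − (1 − s)^22: 20% for s = 1%, 36% for s = 2% and 68% for s = 5%.

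**Specificity.** If a share x of non-bleeders is imputed as false positive, the expected specificity is 0.95 × (1 − x). The limits below are logit limits with n = 1,448, without the centre effect.

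| x | Specificity | Lower limit | Above 0.65? |
|---|---|---|---|
| 0% | 95.0% | 0.938 | yes |
| 10% | 85.5% | 0.836 | yes |
| 20% | 76.0% | 0.737 | yes |
| 28% | 68.4% | 0.659 | yes |
| 29% | 67.5% | 0.650 | borderline |
| 30% | 66.5% | 0.640 | no |

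The smallest passing count is 977 true negatives of 1,448 (67.5%). The switch is therefore at x = 1 − 0.6747/0.95 = 0.29, about 420 patients. If short recordings simply count as negative, specificity stays near 95%.

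**The case against.** The strongest defence is that the two rules have different subjects. Section 4.1 would define the data window from which a result is derived, and 12.1.2 would cover only patients with no usable result. That reading is coherent, but the protocol does not state it, and the word inconclusive in 12.1.2 reaches further than no recording at all. Under section 12.4, patients never monitored are outside the full analysis set, so failed or truncated recordings are largely what is left to impute (sections 6.2.1 and 12.1.2 define the set without that condition).

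It can also be said that details are left to the SAP. Section 12 does leave the censoring of time-to-event variables to it, but the primary endpoint is not one, and the issue is two rules already stated.

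Three stronger conclusions are tempting, and the documents do not support them:

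- **That the rules necessarily give opposite results.** Below about 29% imputed non-bleeders, and with no affected bleeder, the decision is the same. A recording that crossed 12 mmHg before it stopped need not differ between the rules.
- **That the conflict reaches every patient because removal is planned within 48 h.** This rests on 3.3.1 alone. Section 7.1 is looser, and 4.1 treats early stopping as affecting some patients and foresees recordings beyond 48 h. A recording that runs to its planned removal is not plainly missing.
- **That censoring lets a bleeder be dropped.** That contradicts the ITD analysis set. The sensitivity reversal needs the other reading, in which the patient stays in the set but the later bleed is not counted.

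It also stands that the exact interval for 21/21 is not the planned method.

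**Conclusion.** The point holds as an unresolved conflict between two stated rules for the primary endpoint. A short recording without a crossing has no single classification, and neither does a bleed after the last measurement.

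The effect on the decision is conditional. Specificity has a wide margin: the decision changes only at about 29% or more imputed non-bleeders, given 95% true specificity, n = 1,448 and no centre effect. Nothing in the protocol shows that such a share is expected. Sensitivity has almost no margin: with 22 events, one patient separates failure (21/22) from success (21/21), but only if censoring is taken to mean that a bleed after the last measurement is disregarded. If it means negative so far, the two rules agree on sensitivity.

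**What to change.** Replace the censoring sentence in 4.1 with one rule, repeated in 12.1.2 and consistent with the ITD principle:

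1. A crossing of the cut-off before the recording stops is a positive result.
2. A recording without a crossing up to planned removal is a negative result.
3. A recording that ends earlier, through device failure or unplanned removal, without a crossing is inconclusive and imputed as in 12.1.2.
4. A confirmed bleed within 48 h without a prior crossing is a false negative, including a bleed after the sensor stopped.

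Report the version in which no recorded crossing counts as negative as a sensitivity analysis. Reconcile the removal and run times in 3.3.1, 7.1, 7.1.1 and Appendix VI, and their starting point, because item 2 depends on a defined planned removal. Settle this before the pressure data are opened.

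The cost is protocol and SAP wording. Reported specificity may be slightly lower than if short recordings simply counted as negative. Item 3 is also strict on a device that fails shortly before planned removal, and the sensitivity analysis will show how much that matters.

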4.2 Secondary Endpoint Parameters

Secondary endpoint parameters are defined as:

- EP3. Safety of the use of the diagnostic IP by means of adverse events within 1 month following thyroid surgery.
- EP4. Sensitivity and specificity of the IP for detection of clinically relevant hemorrhage within 48 hours following thyroid surgery in a three-level decision system using 10 and 20 mmHg of pressure as cutoffs compared to detection in routine clinical care.
- EP5. Positive and negative predictive values of the IP for detection of clinically relevant hemorrhage within 48 hours following thyroid surgery using the two-level and the three-level decision system compared to detection in routine clinical care.

Clinically relevant hemorrhage and serious adverse events will be adjudicated by an independent Endpoint Review Committee (ERC) according to standardised definitions [7] given in the ERC charter. Outcome death in follow-up will be assessed as equivalent endpoint to clinically relevant hemorrhage.

Parameters relevant for endpoints within the test treatment study (stage 2) are collected within HEDOS study (diagnostic accuracy study, stage 1), too, e.g. clinical symptoms triggering surgical intervention of a suspected post-operative hemorrhage detected in routine clinical care, time to clinical or technical alerts, surgical interventions which did not show post-operative hemorrhage needing intervention.

5. Study Design

In general, the development of a diagnostic test is structured in four phases [1]. In phase I, the functionality and safety of the diagnostic test is examined. In phase II, the diagnostic test is applied to individuals with known disease status to define the cut-off value. Phase III evaluates the diagnostic accuracy based on the pre-defined cut-off value in patients with unknown disease status. Phase IV aims to determine patients' benefit of the test-treatment combination. Hence, the last two phases of the development process are combined. Two single studies are planned to be combined into a phase III/IV seamless design in which a confirmatory phase III diagnostic accuracy study (stage 1) and a subsequent phase IV cluster randomised test treatment study (stage 2) are connected to each other and data from the diagnostic accuracy study will also be used for the randomized test treatment study.

HEDOS represents stage 1 of the seamless design and is planned as a prospective, single-arm, multi-centre, blinded, observational, diagnostic accuracy study with a diagnostic medical product. The occurrence of a post-operative hemorrhage with need for intervention, detected in routine clinical care, is considered as gold standard. It will be conducted in Germany and Austria with about 50 clinical sites participating. The study has a planned number of n=1,470 enrolled and measured patients within a follow-up period of 1 month after end of index thyroid surgical procedure. It is expected to observe about 22 cases of clinically relevant hemorrhage within 48 hours following thyroid surgery within the trial.

It is expected that patient recruitment is completed after about 12 months from the time the first patient is enrolled. The clinical phase of the trial will end about 1 month after the last patient has been enrolled and measured.

Further, a blinded sample size re-calculation based on the incidence of bleeding events measured by the gold standard procedure within the stage 1 study is planned (see section 12.3 for further details).

The randomized test-treatment study in stage 2 will be planned as a multi-center, confirmatory, prospective, parallel-group phase IV diagnostic cluster randomized test-treatment trial comparing the effectiveness of the IP detector vs. routine clinical care monitoring in a consecutive sample of patients undergoing a thyroid surgery. In the first step, all study sites will be randomized to either apply the IP detector (intervention group) on patients undergoing thyroid surgery or to perform routine clinical care monitoring (control group).

Hereby, the control group information is augmented with information coming from the phase III trial in stage 1 [21, 22, 23]. Since these patients are monitored in a routine clinical way and further receive treatment according to current routine clinical care standards anyway, serious heterogeneity with the control arm of the stage 2 study is not expected. Thus, the focus of patient enrolment will mainly be on recruiting study sites and their eligible patients into the intervention group.

It is expected that results of the diagnostic accuracy study (stage 1) will gain new insights into incidence proportion, time course, and strength levels of hemorrhage following thyroid surgery as detected by means of continuous pressure monitoring compared to detection by clinical symptoms, only. The rate of potentially relevant but subclinical hemorrhage without triggering symptoms is unknown yet. This is also applying for the time course and final stages of subclinical but potentially harmful hemorrhage.

Hence, after completion of stage 1 of the seamless design and after market approval of the medical device an unblinded interim analysis is carried out estimating the diagnostic accuracy of the detector and the incidence of alerts in both arms. Thereafter, based on this incidence a sample-size re-estimation is performed in order to derive the required sample size in the standard monitoring arm of stage 2.

The subsequent test treatment study (stage 2) uses the three-level decision system derived from the diagnostic accuracy study (stage 1):

- green phase representing safe conditions without any indication for clinical intervention,
- yellow phase alerting distinctive increase in pressure measures which indicates necessity of intensified monitoring of the patient and stand-by of the surgery team but without clear indication of clinical intervention,
- red phase with serious pressure increase above alert level indicating the need of instantaneous clinical intervention.

The relevant primary endpoint for the test treatment study (stage 2) will therefore be defined by the total incidence proportion of first alerts, technical (three-level decision system) and clinical (clinical symptoms triggering surgical intervention), because both will lead to improvement of clinical outcome of post-surgery patients: either by instantaneous clinical intervention or by intensified monitoring and stand-by of the surgery team providing a prepared subsequent instantaneous clinical intervention.

Figure 1 shows the seamless design graphically.

The subsequent stage 2 study will be described in detail in a separate study protocol with reference to this document, to be finalised after the results of the first study are available.

Figure 1: The confirmatory diagnostic accuracy phase III study and the phase IV randomized test-treatment study are connected via the seamless design. The Effective Sample Size represents the stage 2 prior informativeness in terms of the hypothetical number of stage 1 study centres available for information borrowing [24]. The sample sizes in stage 2 displayed here are exemplary and serve to illustrate the design. The final numbers are calculated in the final analysis of stage 1.

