9.3 Follow-up

The day of index thyroid surgery is day 1 of follow-up on primary and secondary endpoints.

Each patient will be followed until one month after day of index thyroid surgery (\pm 7 days related to visit schedules as displayed in the e-CRF) or until withdrawal of consent (WOC) or death.

9.3.1 Clinical follow-up after 1 month using patient questionnaires

One month after day of index thyroid surgery (± 7 days related to visit schedules as displayed in the e-CRF) or triggered by documentation of withdrawal of consent (WOC), three questionnaires will be sent to the patients by their corresponding study sites together with toll-free envelopes for reply. Patients will be asked to:

- Complete the EQ-5D-5L and the GAD-7 questionnaires
- Document clinical events in a FU questionnaire which are suspicious as AEs.

In case of missing reply after one written reminder by the study site, the patient will be contacted by the study site by phone in order to obtain the required information.

In case a patient reports a clinical event, which is suspicious as SAE, the responsible study site will contact the patient's family doctor, and / or the hospital where the patient was treated, and ask for supporting documents (i.e. hospital discharge letter, diagnostic reports) as applicable. The study site is responsible for completion of the reported event data in the e-CRF.

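### The death rule in Protocol 4.2 has no cause or time limit and conflicts with the disease definition, so an unrelated death may be counted as a false negative in EP1

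*Protocol*

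**What the plan says.** Protocol section 4.1 sets the first primary endpoint as "Sensitivity and specificity (co-primary) of the IP for detection of clinically relevant hemorrhage within 48 hours following thyroid surgery using 12 mmHg" as the cut-off. Its definition of true disease is "surgical intervention triggered by suspicion of a post-operative hemorrhage detected in routine clinical care which is intraoperatively confirmed as needed". Section 12.1.2 repeats this for the diseased individual in the primary model: "surgical intervention performed which confirmed post-operative hemorrhage needing intervention". Neither place names death.

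Section 4.2, in the paragraph on adjudication by the Endpoint Review Committee (ERC), adds: "Outcome death in follow-up will be assessed as equivalent endpoint to clinically relevant hemorrhage". It gives no cause and no time window.

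Section 9.3 states the length of follow-up: "Each patient will be followed until one month after day of index thyroid surgery". It also states what follow-up is for: "The day of index thyroid surgery is day 1 of follow-up on primary and secondary endpoints". Section 15.1.3 has the ERC adjudicate both primary and secondary outcomes. Section 7.1 has the sensor removed at about 48 hours. For measurements that end early, section 4.1 says "data will be censored at the time of last measurements available".

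**The concern.** Section 4.1 treats clinically relevant hemorrhage and true disease as the same thing. Section 4.2 then makes death in follow-up equivalent to that same term. Its place under the secondary endpoints does not confine it, because follow-up serves the primary endpoints too and the ERC adjudicates both.

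Read as written, a patient who dies of another disease during the month could enter the diseased group. The sensor had no bleed to detect, so the expected result is a reading below 12 mmHg and a false negative. If that patient's pressure data were missing or inconclusive, the imputation in section 12.1.2 could lead to the same place.

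The sensitivity claim rests on about 22 events, so a single extra miss matters. If EP1 fails, EP2 also loses its confirmatory status.

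**Working it through.** **Inputs from the protocol (sections 12.1.2 and 12.2).** N = 1,470; prevalence 1.5%; 22 events; assumed sensitivity 0.99; minimum 0.80; two-sided 5%; success if the lower 95% limit exceeds 0.80. Section 3.1 says up to 0.6% of patients with bleeding die. No 30-day all-cause mortality is given, so rates r of 0.01%, 0.05% and 0.1% are assumed.

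**1. The plan's own figure.** Power = Φ[((0.99 − 0.80)√22 − 1.96·√(0.80·0.20)) / √(0.99·0.01)] = 85.9%, against the stated 86%. Events: 1,470 × 0.015 = 22.05. The plan's figure is reproduced.

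**2. How many misses EP1 tolerates.** The Clopper-Pearson lower limit is the 2.5% quantile of Beta(x, n − x + 1). Wilson and ordinary logit limits are shown beside it, all without the centre effect.

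| Detected / diseased | Clopper-Pearson | Wilson | Logit |
|---|---|---|---|
| 22/22 | 0.846 | 0.851 | not computable |
| 21/22 | 0.772 | 0.782 | 0.739 |
| 22/23 (one death added) | 0.781 | 0.790 | 0.748 |
| 25/26 (one death added) | 0.804 | 0.811 | 0.772 |

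At 22 events no miss is tolerated by any of the three. One miss is first tolerated at 25 diseased (Wilson), 26 (Clopper-Pearson) or 31 (logit). By Clopper-Pearson, then, one added death does not fail EP1 once 25 or more bleeds have all been detected. With bleeds distributed as Binomial(1,470, 0.015), the chance of 25 or more is about 29%.

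**3. How likely such a death is.** Hemorrhage deaths expected: 0.006 × 22 = 0.13, so deaths admitted by the rule could well be mostly unrelated. P(at least one death) = 1 − (1 − r)^N.

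| Assumed r | N = 1,470 | N = 4,500 (maximum after re-estimation, section 12.3) |
|---|---|---|
| 0.01% | 14% | 36% |
| 0.05% | 52% | 89% |
| 0.1% | 77% | 99% |

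**4. Effect on power at N = 1,470.** Let b be the bleeds, Binomial(1,470, 0.015); d the added deaths, Poisson(1,470·r), all counted and all test-negative; X the detected bleeds, Binomial(b, 0.99). Success means that the Clopper-Pearson lower limit of X/(b + d) exceeds 0.80. Summing P(b)·P(d)·P(success) over b and d gives:

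| Assumed r | Power for sensitivity | Loss |
|---|---|---|
| no deaths counted | 75% | – |
| 0.01% | 68% | 7 points |
| 0.05% | 44% | 31 points |
| 0.1% | 25% | 50 points |

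The start is 75% and not 0.99^22 = 80% because the bleed count varies. With x = n the lower limit is 0.025^(1/n), which is 0.794 at n = 16, so fewer than 17 bleeds cannot pass even with none missed.

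**The case against.** A reader might infer that every unrelated death after sensor removal does become a false negative in EP1. The protocol does not say so. EP1, EP2, EP4 and EP5 are each limited to 48 hours, and the definition of true disease in sections 4.1 and 12.1.2 leaves death out. On that reading a death on day 20 is an equivalent event outside the window and never enters EP1. This stands: the effect on EP1 follows from one of two readings. It does not remove the problem. No endpoint covers hemorrhage over one month, so on the narrow reading the words about follow-up have almost no function. An unrelated death within 48 hours is caught on either reading.

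The ERC charter, which is not at hand, may limit cause and time. But the protocol states the rule without limits, and a charter that narrowed it would depart from the protocol.

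The rule also has a sensible purpose. A patient who dies of neck bleeding without re-operation would otherwise count as non-diseased. That should be kept.

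The size also has limits. A patient who had exceeded 12 mmHg would count as a true positive. One death does not decide EP1 in every case, as the 25/26 row shows.

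A reader might further infer that predictive values and AUC are distorted. That is not supported. A test-negative death leaves crude PPV, TP/(TP + FP), unchanged. It moves crude NPV by about 1/1,400, under 0.1 percentage point. One green-phase case among 23 costs the AUC about 0.02, against a threshold of 0.70.

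**Conclusion.** The conflict between section 4.2 and sections 4.1 and 12.1.2 is real and touches the reference standard of the primary endpoint. The missing cause restriction is a defect on both readings; the missing time limit is one only if later deaths enter the 48-hour endpoints. What is established is that an unrelated death may be counted as a false negative, not that it will be.

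If it is counted at the planned 22 events, EP1 fails by all three intervals checked. The power loss of 7 to 50 points rests on assumed mortality of 0.01% to 0.1%, on every death being counted and test-negative, on exact limits, and on no centre effect. It shows how exposed the endpoint is and is not a forecast.

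**What to change.** Replace the sentence in section 4.2 with a rule such as: *In the accuracy endpoints, a death counts as clinically relevant hemorrhage only if the ERC, blinded to the pressure data, adjudicates it as caused by neck hemorrhage with onset within 48 hours of index surgery. All other deaths are reported under EP3.*

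Carry the same wording into the disease definition in section 4.1, the description of the diseased individual in section 12.1.2, and the ERC charter. This keeps fatal bleeds that were never re-operated in the diseased group.

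The cost is one sentence with matching edits. The ERC already adjudicates these events, and neither the data collected nor the sample size changes.
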